## 5.2 Adverse Event Assessments

### Relatedness:

- Procedure-related: Event has a strong temporal relationship to the study procedure. This includes AEs attributable to any device(s) used at procedure, such as access devices, delivery microcatheters, embolic coils, non-ionic contrast, guidewires, or any other adjunctive, approved/cleared device for treatment of intracranial aneurysms.
- Device-related: Event has a strong temporal relationship to the CorPath GRX System.
- Unknown: Event relationship cannot be attributed to any of the above categories and remains undetermined.

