### 5.3 Procedure-Related Adverse Event

An adverse event is procedure-related when, in the judgment of the Investigator; it is reasonable to believe that the event occurs from the endovascular robotic procedure, irrespective of the device.

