## 13. DEFINITIONS

TERM	DEFINITION
Adverse Event (AE)	Any untoward medical occurrence, unintended disease or injury, or untoward clinical signs (including abnormal laboratory findings) in subjects, users or other persons, whether or not related to the investigational medical device.
Device-Related Adverse Event	Event has a strong temporal relationship to the study device, and alternative etiology is less likely.
Major Stroke	A stroke, which increases the NIHSS of the subject by $\geq 4$ .
Minor Stroke	A stroke, which increases the NIHSS of the subject by $\leq 3$
Transient Ischemic Attack (TIA)	A transient episode of neurologic dysfunction caused by focal brain, spinal cord, or retinal ischemia without acute infarction.
Modified Rankin Scale (mRS)	Scale for measuring general neurologic function. 
 
0. No symptoms at all
 
1. No significant disability despite symptoms; able to carry out all usual duties and activities
 
2. Slight disability; unable to carry out all previous activities, but able to look after own affairs without assistance
 
3. Moderate disability; requiring some help, but able to walk without assistance
 
4. Moderately severe disability; unable to walk without assistance and unable to attend to own bodily needs without assistance
 
5. Severe disability; bedridden, incontinent and requiring constant nursing care and attention
 
6. Dead
 

NIHSS Scale	The National Institutes of Health Stroke Scale, or NIH Stroke Scale (NIHSS) is a tool used by healthcare providers to objectively quantify the impairment caused by a stroke . The NIHSS is composed of 11 items, each of which scores a specific ability between a 0 and 4. For each item, a score of 0 typically indicates normal function in that specific ability, while a higher score is indicative of some level of impairment.  The individual scores from each item are summed in order to calculate a patient's total NIHSS score. The maximum possible score is 42, with the minimum score being a 0
Neurological Deterioration	Defined as $\geq 4$ -point increase compared with baseline in the NIHSS at discharge.
Procedural Related Adverse Event	Defined as events that occur from the endovascular robotic procedure, irrespective of the device.

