4.4.10 Secondary Endpoint 10: Adverse Events

Endpoint: All adverse events (AEs) from the start of the CorPath GRX procedure until the end of the study as recorded on CRF 11 Adverse Event / Serious Adverse Event CRF.

Subjects to Include: Analysis Cohort

Statistical Analysis: The count and percentage of subjects experiencing AEs will be summarized by Adverse Event Term and include breakdowns by seriousness and relatedness to device and procedure.

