4.5 Additional Summaries

Some additional summaries will be prepared:

- Descriptive statistics of the population
 - Demographics and patient baseline characteristics

- Aneurysm characteristics
- Procedures performed
- Malfunctions
- Protocol deviations

5 Data Conventions and Missing Data

It is assumed that because the primary and most secondary analyses are evaluated within twenty-four (24) hours of CorPath GRX procedure or prior to hospital discharge, whichever occurs first, there will be no missing data. For the 90-day and 180-day secondary endpoints (modified Rankin Scale, thromboembolic events, and aneurysm occlusion), all practical monitoring and follow-up steps will be taken to ensure complete and accurate data collection. Additionally, all data collected on safety or adverse events will be reported to the extent they are available.

6 Appendix 1: Adverse Event Classification and Definitions

An Adverse Event (AE) is any untoward medical occurrence, unintended disease or injury, or untoward clinical signs (including abnormal laboratory findings) in subjects, users or other persons, whether or not related to the investigational medical device.

A Serious Adverse Event (SAE), as per the European Standard ISO 14155 (E), is an AE that:

- Led to death
- Led to a serious deterioration in the health of a patient that:
- Resulted in a life-threatening illness or injury
- Resulted in a permanent impairment of a body function or body structure
- Required in-patient hospitalization or prolonged hospitalization
- Resulted in medical or surgical intervention to prevent permanent impairment to a body function or body structure
- Led to fetal distress, fetal death or a congenital abnormality or birth defect.

In the current study indication, a SAE can be defined as an adverse event where the outcome is one of the following:

- Incidence of death 24 hours post procedure
- Target aneurysm rupture
- Vessel perforation
- Vessel dissection
- Thromboembolic complication
- Failure to navigate to target
- Device failure to respond to input, or other intra-operative device failure

Adverse Event Assessments

Relatedness:

- Procedure-related: Event has a strong temporal relationship to the study procedure. This includes AEs attributable to any device(s) used at procedure, such as access devices, delivery microcatheters, embolic coils, non-ionic contrast, guidewires, or any other adjunctive, approved/cleared device for treatment of intracranial aneurysms.

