- Device-related: Event has a strong temporal relationship to the CorPath GRX System.
- Unknown: Event relationship cannot be attributed to any of the above categories and remains undetermined.

Procedure -Related Adverse Event

An adverse event is procedure-related when, in the judgment of the Investigator; it is reasonable to believe that the event is not associated with the CorPath GRX System use and is not specific to the device used. Instead, other products, surgical techniques, or medications required

Device-Related Adverse Event

An adverse event is device-related when, in the judgment of the Investigator, the clinical event has a reasonable time sequence associated with use of the CorPath GRX System and is unlikely to be attributed to concurrent disease or other procedures or medications. It is reasonable to believe that the CorPath GRX System directly caused or contributed to the adverse event.

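### SAP Appendix 1 excludes CorPath-associated events from procedure-related adverse events while protocol 5.3 includes them, and neither document's relatedness scale lists a not-related level.

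*SAP*

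**What the plan says.** **Procedure-related, protocol.** Section 5.3 applies the label when, in the investigator's judgement, "it is reasonable to believe that the event occurs from the endovascular robotic procedure, irrespective of the device". The glossary in Section 13 agrees: "Defined as events that occur from the endovascular robotic procedure, irrespective of the device".

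**Procedure-related, SAP.** Appendix 1 requires a belief that "the event is not associated with the CorPath GRX System use and is not specific to the device used". The sentence after it breaks off in the text available here. That may come from the PDF conversion and is not counted against the plan. The excluding clause itself is complete.

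**The scale.** Protocol 5.2 and SAP Appendix 1 list the same three levels. The first is "Procedure-related: Event has a strong temporal relationship to the study procedure", to which both documents add: "This includes AEs attributable to any device(s) used at procedure". The second is device-related, meaning CorPath GRX. The last is "Unknown: Event relationship cannot be attributed to any of the above categories and remains undetermined". No level for unrelated events is listed.

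**Use.** SAP 4.4.10 (secondary endpoint 10) counts subjects with AEs, from the start of the procedure to the end of the study, by term. The summary is to "include breakdowns by seriousness and relatedness to device and procedure".

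**The concern.** The SAP and the protocol give different membership rules for one column of a safety table. In a single-arm study of a robotic system, the events on which the rules disagree, those associated with the robot, are the ones a reader of that table will look for. A programmer or report writer working from the SAP would either attach a definition that does not match how the data were coded, or apply that definition and move events between columns.

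The second gap is in the scale. AEs are recorded whether or not they are related to the device, and they are collected through 180 days. Some will plainly have nothing to do with the procedure or the robot. The only listed level that is neither procedure- nor device-related is the one for undetermined events, and a clearly unrelated event is not undetermined. If such events are put there, the table cannot separate doubt about causality from confidence that there was none.

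**Working it through.** The plan states no figure on this point, so there is none to reproduce. The check is a comparison of definitions, followed by an illustration on assumed counts.

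**Step 1. Where the two definitions agree and differ**

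| Type of event | Protocol 5.3 and glossary | SAP Appendix 1 definition |
|---|---|---|
| From access, contrast or technique, robot not involved | procedure-related | procedure-related |
| From the robotic procedure, associated with CorPath use | procedure-related | not procedure-related |
| Unrelated to procedure and robot | not procedure-related | not procedure-related |

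They differ in the second row only.

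**Step 2. Which rule governs coding.** Protocol 5.5 says AEs are categorised by the definitions in protocol Sections 5.1 to 5.4. SAP 4.4.10 takes events as recorded on CRF 11, and nothing in the SAP instructs recoding. The natural reading is that the table follows protocol coding and the SAP definition describes it incorrectly.

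**Step 3. Effect if the SAP definition were applied.** Let P be the number of subjects with a procedure-related AE under protocol 5.3. Let k be the number of those whose only such AEs are CorPath-associated. Then:

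- protocol count = P
- SAP count = P − k
- difference = k

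Assume for illustration 108 subjects and P = 20. Neither P nor k comes from the plan. Exact 95% limits are the Beta(x, n − x + 1) quantile at 0.025 and the Beta(x + 1, n − x) quantile at 0.975, with the lower limit set to 0 when x = 0.

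| k | Protocol 5.3 | SAP Appendix 1 |
|---|---|---|
| 0 | 20/108 = 18.5% (11.7 to 27.1%) | 20/108 = 18.5% (11.7 to 27.1%) |
| 5 | 20/108 = 18.5% (11.7 to 27.1%) | 15/108 = 13.9% (8.0 to 21.9%) |
| 10 | 20/108 = 18.5% (11.7 to 27.1%) | 10/108 = 9.3% (4.5 to 16.4%) |
| 20 | 20/108 = 18.5% (11.7 to 27.1%) | 0/108 = 0% (0 to 3.4%) |

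The tables agree when k = 0 and separate by exactly k.

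**Step 4. Where an unrelated event goes.** Take a clearly unrelated illness late in follow-up. It is not procedure-related. It is not device-related, because protocol 5.4 and the SAP both require a reasonable belief that the system caused or contributed to it. It is not unknown, because its cause is not in doubt. The listed scale is exhausted.

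**The case against.** The strongest reply is that protocol 5.5 settles the coding rule, so the SAP wording may never touch the data. That stands. A reader might infer that the endpoint 10 table is bound to be wrong. The documents support only that it would be misdescribed, or shifted if the SAP rule were applied and CorPath-associated events occurred.

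A reader might also call the two definitions opposites. They are not: they part company only on CorPath-associated events. Nor is the SAP plainly at odds with its own relatedness list. That list names access devices, coils, contrast and similar items, and it gives CorPath a separate level, so it can be read as dividing CorPath from everything else.

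Nor would robot-attributed events disappear. They would normally appear as device-related, and they stay in the totals by term and seriousness. One qualification applies: the fuller device-related definition requires that other procedures or medications be an unlikely cause. An event with both a robotic and another procedural explanation could therefore miss both SAP definitions, whereas protocol 5.3 would count it.

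On the scale, protocol Section 5 has relationship to device and relationship to procedure evaluated, and CRF 11's response options are not in the documents, so a *no* to each may be available. Protocol 5.8 lets the Surveillance Committee attribute events to the subject or to disease. Both points stand, and they rule out inferring that every unrelated event will be shown as undetermined. They do not close the gap: the written scale lacks the level, and SAP 4.4.10 does not say whether investigator or committee attribution is tabulated.

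**Conclusion.** The point holds in a limited form. The SAP definition conflicts with the protocol definition used to code events, and the scale written in both documents has no correct place for a clearly unrelated event.

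The size depends on two counts that the plan does not give: subjects whose only procedure-related events are CorPath-associated, and unrelated events during follow-up. It is tempting to apply the plan's 5% safety rate to 108 subjects (0.05 × 108 = 5.4) and say that about 5 would change category. The documents do not support that. The 5% is 30/626 = 4.8% rounded, from a coil trial used as the historical manual control. It is not a robot-related AE rate. It was set for the peri-procedural primary composite, whereas endpoint 10 covers all AEs to the end of the study. The figure would also need every such event to be CorPath-associated and the SAP definition to override protocol 5.5.

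The consequence is confined to a descriptive secondary safety summary with no hypothesis or decision rule. The primary safety endpoint counts named events and does not use this scale. The sample size and power are unchanged.

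**What to change.** 1. Replace the procedure-related definition in SAP Appendix 1 with the one in protocol 5.3.
2. In protocol 5.2 and the SAP, make relatedness to device and relatedness to procedure two separate items, each with a *not related* level, so that an event can be related to both, one or neither. Add the level to CRF 11 if it is absent.
3. State in SAP 4.4.10 whether the investigator's or the Surveillance Committee's attribution is tabulated.

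The cost is wording changes in the protocol and SAP, possibly one CRF change, and a review of any events already coded as unknown. This is best done before the AE tables are produced.
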